## 1. List of abbreviations

AL	axial length
MD	myopic defocus
MI	masked investigator
MS	multi-segment
IOP	intra-ocular pressure
PD	Pupillary distance
Rx	refractive error
SER	spherical equivalent refraction
SFCT	subfoveal choroidal thickness
SD	standard deviation
SD-OCT	spectral Domain Optical Coherence Tomography
SV	single vision
UMI	unmasked investigator

## 2. Protocol Summary

Title	The Clinical trial of myopia control for children using the Multi-segment (MS) lens
Venue of data collection	Centre for Myopia Research, School of Optometry, The Hong Kong Polytechnic University
Application of device	Myopia (shortsightedness) myopia in children and youngsters
Study design	2-year prospective, randomized and double-masked clinical study
Primary outcome	Changes in cycloplegic autorefraction (diopters, D)
Secondary outcome	Changes in axial length (mm)
Rationale for Number of Subjects	Treatment group: 90 Control group: 90
Subject criteria	
Inclusion criteria:
 
 
• Hong Kong Chinese
 
• Age at enrolment: 8-13 year.
 
• Spherical equivalent refraction (SER): -1.00 to -5.00D
 
• Astigmatism and anisometropia: 1.50 D or less
 
• Spectacle corrected monocular VA: 0.0 logMAR or better
 
• No strabismus: checked by cover test at far and near.
 
• No prior treatment of myopic control, e.g. orthokeratology, progressive addition lenses, bifocal lenses, drugs (e.g. atropine), etc.
 
• Willingness to wear spectacle lenses regularly
 
• Parents' understanding and acceptance of random allocation of grouping
 
 
Exclusion criteria
 
 
• Any ocular and systemic diseases and abnormalities might affect visual functions or refractive development
 
Any eye pathology and conditions
 

Intervention device / Treatment	Multi-Segment (MS) lens (re-named as Defocus Incorporated Multiple Segments (DIMS) spectacle lens later)
Control	Control: single vision (SV) spectacle lens
Wearing module	Full-day wear
Visits of the study /main data collection	Baseline visit, follow-up visits every 6 months for 2 years Total: 5 data taking visits

## **The Clinical trial of myopia control for children using the Multi-segment (MS) lens**

### **3. STUDY RATIONALE AND OBJECTIVES**

#### **3.1 Background**

Myopia (also called ‘shortsightedness’) is a common refractive eye disorder. The prevalence of myopia is alarmingly high in many Asian countries such as Hong Kong and Singapore, as many as 80% of young adults is myopic.  There is a trend of increasing prevalence of myopia and increasing severity of myopia in the last decade. Myopic eyes are prone to a number of ocular diseases, such as retinal degeneration and glaucoma, which can lead to severe visual impairment. 

We have invented a contact lens, ‘Defocus Incorporated Soft Contact (DISC) lens’, for slowing progression of myopia in children. The DISC lens is a bifocal soft contact lens and is designed by the principle of simultaneous defocus. It provides clear vision and constant myopic defocus simultaneously for wearers in all viewing distances. The recent study has shown that DISC lens slowed myopia progression up to 50% in Hong Kong schoolchildren. 

The Hong Kong Polytechnic University and Sponsor (a lens company) have jointly invented a spectacle lens design using simultaneous defocus principle -Multi-Segment (MS) lens. The sponsor is able to manufacture the technical design which aims at correcting distance vision and at the same time producing MD images on the retina for all distances in the form of a spectacle lens. The MD aims at slowing down myopia progression. The purpose of this study is to investigate if the MS lens can slow myopia progression in schoolchildren.

#### **3.2 Aims of the study**

- To determine if wearing the MS lenses slows the progression of myopia and axial elongation in myopic schoolchildren over 2 years.
- To compare the changes in refractive error (Rx) and axial length (AL) in children wearing MS lens with those children wearing single vision (SV) spectacle lens (control).

## **4. METHODS AND STUDY DESIGN**

### **4.1 Subjects: inclusion and exclusion criteria**

Hong Kong Chinese myopic children aged from 8-13 years will be recruited in this study. This age range is selected because myopia progression rate has been found to be fastest compared with other ages and the mean progression rate in myopic children is about 1D annually.

#### Inclusion criteria

Specific inclusion criteria are as follows:

- Ethnicity: Hong Kong Chinese
- Age at enrolment: 8-13 years
- Spherical equivalent refraction (SER): -1.00 to -5.00 Dioptres (D)
- Astigmatism and anisometropia of 1.50 D or less
- Spectacle corrected monocular VA: 0.0 logMAR or better
- Free of ocular and systemic abnormalities might affect visual functions or refractive development
- Willingness to wear spectacle lenses regularly
- Parents' understanding and acceptance of random allocation of grouping

#### Exclusion criteria

- Any ocular and systemic diseases and abnormalities might affect visual functions or refractive development

Any history of prior myopia control treatment, e.g. orthokeratology, progressive addition lenses, bifocal lenses, drugs (e.g. atropine), etc.

### **4.2 Study Design**

This is a 2-year prospective, randomized and double-masked clinical trial. After visual screening, the children are fulfilled the inclusion criteria will be enrolled in the study. The children will be randomly allocated to wear either MS lenses or regular SV spectacle lenses. Allocation will be determined by a random software sequence in Excel.

Their refraction and AL will be followed up every 6 months over 2 years: baseline, 6-, 12-, 18- and 24-month visits. The changes in cycloplegic refraction and AL between two groups of children will be compared. Data collection will be performed in Centre for Myopia Research, the Hong Kong Polytechnic University (PolyU). Written assent and informed consent will be obtained from children and their parents before participation respectively.

### **4.3 Sample size estimation**

The number of subjects required for the clinical trial is based on the power calculation for subject numbers. We use 90% power to detect 0.50D difference (with 0.6D of standard deviation (SD)) in myopia progression between two groups with a significance alpha level of 0.01 (2-tailed); the minimum subject number required to complete the study in each group is 43. Assuming a conservative dropout rate of about 40%, 72-75 children are required in each group.

The project will recruit altogether 180 subjects: 90 for control group and 90 for experimental group.

#### **4.4 Spectacle lenses**

##### MS lenses and spectacle prescription

The MS lens is a custom-made plastic spectacle lens. The lens power matches distant prescription. There are multi small defocusing zones of relatively positive embedded in the lens. Such design allows to introduce MD and to maintain clear vision simultaneously. The controls are the ordinary SV spectacle lenses are made of 1.6CR39HMC.

The final distance prescription of spectacles is determined on cycloplegic subjective refraction. The children will be instructed to wear lenses all the time.

*Treatment group: MS spectacle lenses*

*Control group: SV spectacle lenses*

#### **4.5 Randomization process**

A simple randomization will be adopted in this study. Group allocation will be determined by the random sequence generated by Excel.

#### **4.7 Study outcomes and its measurement**

##### Primary outcomes

- Changes in auto-refraction (SER in diopters) with cycloplegia

##### Secondary outcomes

- Changes in axial length (mm) with cycloplegia

Refraction and AL under cycloplegia will be measured at baseline and at six-month intervals for 2 years. One drop of proparacine 0.5% and then 1-2 drops of cyclopentolate HCL 1 % will be instilled to induce cycloplegia. Cycloplegic refraction will be measured by the open-field autorefractor (Shin-Nippon NVision-K 5001 autorefractor). Five measurements are obtained for each eye. The SER of the representative value from these 5 readings was used for statistical analysis. AL will be measured by IOL Master (Carl Zeiss) Five measurements will be taken and then averaged.

[figure not shown]
Myopia progression (change in refraction) over 2 years will be determined by the difference between SER (from cycloplegic autorefraction) at the fifth and the first (baseline) visits.

## 4.8 Study visits, eye examination procedures

**Figure 4.1** illustrates the overall plan of visits throughout the study. The participating children and their parents (or guardians) go through screening phone call, vision screening, baseline examination, lens delivery visit, contact lens follow-up visits and 4 comprehensive eye examinations (main data collection) at study months 6, 12, 18 and 24 months.

### 4.8.1 Subject recruitment and phone screening

The subjects are recruited through placing posters, public media and the study website. The screening phone call are carried out for recruit potentially eligible subjects, to exclude children who are not eligible, such as asking for age of the child, history of recent eye exam, spectacle prescription, etc. Then, a vision screening will be schedule vision screening for the potential children to confirm if they really fit for our study criteria (depend the schedule of the subject).

**Figure 4.1** Overall plan of different visits in the study

#### 4.8.2 Pre-baseline visual screening, baseline and main follow-up visits

Some screening tests are performed to determine if the children fit for our study criteria. The pre-baseline screening tests include: autorefraction, cover tests, non-contact IOP, subjective refraction, best corrected VA and external ocular health exam by slit-lamp.

If the subjects pass the screening tests, they and their guardians will be asked to sign the consent if they agree to join the clinical trial after explaining the nature and details of the study by UMI. Then the participated children will have a comprehensive eye examination and baseline data measurement without and with cycloplegia. These procedures will be repeated every 6-month over 2 years. Key baseline measurements included refraction, axial length (AL), keratometry and phoria biometry will be undertaken either at the same time as the vision screening session or in a follow-up session.

The lists of the study procedures and measurements to be performed at different visits and is summarized in **Table 4.1**. All the data collection will be conducted at our Optometry Research Clinic, School of Optometry, the Hong Kong Polytechnic University.

The following measurement and eye tests will be performed by MI at baseline, 6, 12, 18 and 24M visits (5 visits over 2 years).

##### Without cycloplegia

- Determination of dominant eye
- Subjective and objective refraction
- Best corrected visual acuity
- Corneal curvature/ topography
- Binocular vision tests: phoria tests, stereopsis
- Accommodative tests: amplitude of accommodation, lag of accommodation with 3D stimulus
- Pupil diameters under different illumination, during distance and near viewing
- Non-contact IOP
- Subfoveal choroidal thickness (SFCT) by Spectral Domain Optical Coherence Tomography (SD-OCT)

##### With cycloplegia

- Subjective refraction (as reference for the prescription of contact lenses)
- **Objective refraction:** measured by using Shin-Nippon NVision-K 5001 (open-field) autorefractor. Five measurement are obtained for each eye and the average of SER of was used for statistical analysis.
- **AL measurement:** measured by IOL Master (Carl Zeiss). Five measurements were taken and averaged.
- Peripheral refraction: measured by using a Shin-Nippon NVision-K 5001 autorefractor at center, 10, 20 and 30 degrees at the nasal and temporal visual field across the horizontal meridian.
- Dilated fundus examination

Table 4.1 Examination procedures/ items for each visit.

Procedures /measurements	*Screening	Baseline	2 wk	1M	3M	6M	12M	18M	24M
Consent form signed		x							
History-initial	x	x							
History-Update			x	x	x	x	x	x	x
Non-cycloplegic autorefraction	x	x				x	x	x	x
Habitual spec VA	x	x				x	x	x	x
Subjective refraction	x	x				x	x	x	x
Best-corrected VA	x	x				x	x	x	x
Cover test (distance, near)	x								
Phoria (distance and near)		x				x	x	x	x
Lag of accommodation		x				x	x	x	x
Amplitude of accommodation		x				x	x	x	x
Stereopsis		x				x	x	x	x
Pupil size		x				x	x	x	x
Keratometry		x				x	x	x	x
Slit-lamp exam, external ocular health check	x	x				x	x	x	x
IOP measurement	x	x				x	x	x	x
Choroidal thickness measurement		x	x	x	x	x	x	x	x
Eye drops: Anesthetic, Cycloplegics		x				x	x	x	x
Cycloplegic subjective refraction		x				x	x	x	x
Cycloplegic autorefraction		x				x	x	x	x
Axial length measurement		x				x	x	x	x
Peripheral refraction		x				x	x	x	x
Dilated fundus exam		x				x	x	x	x

VA with habitual spectacle			X	X	X	X	X	X	X
Questionnaire of visual habits and spectacle lens performance									X

\* Screening day may be at the same day of baseline measurement.

### 4.8.3 Spectacle prescription and visual performance of lenses

The final distance prescription of spectacles is determined on cycloplegic subjective refraction performed by the masked optometrist. UI do frame adjustment, mark and measure PD and fitting heights for all subjects whatever they are wearing MS lenses or SV lenses because the subjects are masked from the grouping.

Visual performance, including visual acuity at distance and near under high and low contrast, with spectacle lenses will be assessed at the first delivery visit. Subject will wear lenses on a daily

The lens will be replaced and upgraded if the equivalent sphere of refraction (SER) is changed by 0.5D or more (or habitual aided LogMAR VA worsen than 0.2) in either eye as compared with wearing spectacle refraction. The children will be instructed to wear lenses all the time throughout the study. Aided VA at both distance and near will be measured in delivery of new spectacles.

### 4.9 Questionnaire

Parents or guardians will be complete a questionnaire regarding the child's vision habits and parents' Rx, and the number of years that the child has been myopic before they enroll in this trial. Questions regarding how much time the children spend reading and outdoor activities will be included. In addition, patient-reported measures on lens performance are also assessed using questionnaire.

### 4.10 Visual performance of lenses

Visual performance tests of the lenses will be carried out in the visit of contact lens delivery. The items include:

- Objective Visual Assessment
  - Distance and near visual acuity in low and high contrast:
  - Binocular vision tests:
    - Horizontal phoria at distance and near
    - Stereoacuity (minute of arc)
    - Amplitude of accommodation (D)
    - Lag of accommodation

- Patient-Reported Measures of Lens Performance using questionnaire.

#### 4.11 Statistical analysis

Data of two groups will be presented as the mean  $\pm$  SD. Only data of the right eyes will be used for data analysis if there are high correlation of data between two eyes. Baseline data between two groups between males and female will be analyzed by unpaired t-tests. Welch correction is applied if the difference of SD between the groups is statistically significant.

Primary outcomes

- Changes in auto-refraction (SER in diopters) with cycloplegia

Secondary outcomes

- Changes in axial length (mm) with cycloplegia

1. Repeated measures ANOVAs were used to compare the changes from the baseline visit in SER, and AL over time and between the two study groups in study. Interactions between time and groups were also assessed. If repeated measures ANOVA showed significant results between groups and significant interaction between time and groups, unpaired *t* tests were used to test for differences in SER, AL, between the two groups after the 24-month follow up period, and plots of the change will be plotted for showing trends. Bonferroni corrections were used to take account of *post-hoc* comparisons. The efficacy of myopic control will be determined by dividing the difference in mean SER changes of two groups with the mean SER change in the SV group times 100%.
2. The correlations between changes in Rx, biometric parameters and related factors (e.g. lens wear time, time spent on outdoor activities) are analyzed using Pearson correlations. Multivariate analyses of variance are used to examine the effect on treatment outcomes of various factors, including age, gender, initial refraction, etc.
3. To examine the choroidal response to MD in MS lens, changes in choroidal thickness over time and between two groups will be compared by the same statistically methods used for SER and AL mentioned above (*point 1*). Besides, the correlation between changes in choroidal thickness and axial length will be calculated using Pearson's correlation coefficient. Correlation between the pupil sizes, peripheral refraction and the effect in myopic control in terms of axial length elongation will be calculated using Pearson's correlation coefficient.

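### Section 4.11 lets an undefined 'high' inter-eye correlation decide whether the primary outcome is analysed on right eyes only, and gives no method for the other case

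*Combined protocol and SAP*

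**What the plan says.** The rule is one sentence in section 4.11: "Only data of the right eyes will be used for data analysis if there are high correlation of data between two eyes". The primary outcome in section 4.7 is "Changes in auto-refraction (SER in diopters) with cycloplegia", with no study eye named. The same section provides readings from both eyes: "Five measurements are obtained for each eye". Sections 5.1 and 5.13 repeat this. Dominant eye is recorded (section 5.2) but is not linked to any analysis.

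For the comparison itself, section 4.11 says "Repeated measures ANOVAs were used to compare the changes from the baseline visit in SER, and AL over time" and between groups. Depending on those results, unpaired t "tests were used to test for differences in SER, AL, between the two groups after the 24-month follow up period". No eye term, per-child average or clustering by child is described for either method.

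The sample size in section 4.3 counts children: "We use 90% power to detect 0.50D difference", with an SD of 0.6 D, "with a significance alpha level of 0.01 (2-tailed", giving 43 completers per group. Section 4.11 does not restate the significance level.

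**The concern.** The condition, "high correlation of data between two eyes", is not operational. It could refer to baseline SER, change in SER or axial length; to one visit or all of them; to arms pooled or separate; and to any cut-off. Two competent analysts could follow the plan faithfully and analyse different data for the primary comparison.

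The word 'only' suggests that something other than right eyes alone is used when the correlation is not high, but the plan does not say what. The listed tests take observations from different children as independent and, as described, have no place for two eyes of one child. If both eyes were put into them as separate rows, the standard error would be too small and the strict 1% level used for planning would not hold. If right eyes alone are used, the analysis is sound, but the left-eye measurements add nothing to the precision of the treatment comparison.

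**Working it through.** **Inputs.** From section 4.3: difference 0.50 D, SD 0.6 D, two-sided alpha 0.01, power 90%, 43 completers per group, about 40% dropout, 90 recruited per group. The documents give no inter-eye correlation of change (rho) and no cut-off for 'high'. All values of rho and of the cut-off below are assumptions.

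**1. The plan's own figure.** Normal approximation: n = 2 × (2.576 + 1.282)² × (0.6/0.5)² = 42.9, so 43 per group, and 43/0.6 = 71.7, so 72. The t-based version gives 45, and 45/0.6 = 75. The stated 43 and 72-75 are reproduced, and the planning unit is the child.

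**2. Both eyes entered as independent rows.** The true standard error is sqrt(1 + rho) times the one used, so the actual error is 2 × [1 − Φ(2.576/sqrt(1 + rho))].

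| Assumed rho | sqrt(1 + rho) | 2.576/sqrt(1 + rho) | Actual two-sided error at nominal 1% |
|---|---|---|---|
| 0.5 | 1.225 | 2.103 | 3.5% |
| 0.6 | 1.265 | 2.036 | 4.2% |
| 0.7 | 1.304 | 1.976 | 4.8% |

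Over the wider range 0.3 to 0.95, the same formula gives 2.4% to 6.5%.

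**3. The conditional rule as a whole.** The rule was simulated under no treatment effect for the 24-month t test (40,000 runs, 43 and 90 per arm, nominal 1%, assumed cut-offs 0.7, 0.8 and 0.9).

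- *Low-correlation branch enters eyes as independent rows.* With true rho at the cut-off, each branch is taken about half the time and overall error is about 3.0% to 3.9%. With rho 0.7 and cut-off 0.8, it is about 4.8%. With rho 0.9 and a cut-off of 0.8 or lower, the right-eye branch is practically always taken and error stays at about 1%.
- *Low-correlation branch uses the per-child mean.* Error is about 0.9% to 1.1%.
- *Analyst keeps the smaller p-value of right eye and per-child mean.* Error is about 1.2% to 1.6%.

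**4. Precision of the two-eye mean.** SD of the mean = 0.6 × sqrt((1 + rho)/2). The equivalent gain in children relative to right eye only is 2/(1 + rho) − 1. Power uses the noncentral t at alpha 0.01 for 0.50 D. Expected completers: 90 × 0.6 = 54 per group.

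| Analysis | SD (D) | Equivalent extra children | Power, 43 per group | Power, 54 per group |
|---|---|---|---|---|
| Right eye only | 0.600 | none | 88.7% | 95.4% |
| Mean, rho 0.9 | 0.585 | 2/1.9 − 1 = 5% | 90.5% | 96.4% |
| Mean, rho 0.8 | 0.569 | 2/1.8 − 1 = 11% | 92.2% | 97.2% |

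The 88.7% at 43 differs from the planned 90% only because the plan's 43 matches the normal approximation.

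**The case against.** The strongest defence is that the plan never says both eyes will be entered as separate rows. It is silent on the low-correlation case. A per-child mean, separate analyses by eye or an eye factor would all fit that silence. The condition itself suggests awareness that two eyes of one child are not independent, and section 4.3 plans in children. A reader might infer that the plan prescribes an invalid two-eye test; the text does not support that. This part of the objection stands, so the error figures in step 2 are conditional.

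A reader might also infer that inspecting the correlation in itself spoils error control. Step 3 shows that it does not: with a child-level fallback the error stays near 1%, and even choosing the smaller of two child-level p-values moves it only to about 1.2% to 1.6%.

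Nor is the right-eye branch faulty. It gives one value per child, holds its level and matches the sample-size unit. It applies when the correlation is high, which is where averaging adds least. The left-eye readings also have a use outside the efficacy analysis, because sections 4.8.3 and 5.15 base lens replacement on changes in either eye.

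What the defence cannot supply is a definition of 'high' or a method for the other case. Neither appears anywhere in the documents.

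**Conclusion.** The point holds as a prespecification gap with a cheap improvement attached. The unit of the primary analysis rests on an undefined judgement made on the data, and one of the two outcomes of that judgement has no method.

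An error of about 3.5% to 4.8% at a nominal 1% needs three things together: a correlation judged not high, both eyes entered as independent rows, and a true correlation of about 0.5 to 0.7. The documents establish none of these. If the correlation is clearly high, the right-eye analysis applies and the practical effect on the primary comparison is small.

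The precision available from averaging is modest: about 5% to 11% more children at an assumed correlation of 0.9 to 0.8, or 1 to 2 points of power at the expected 54 completers per group. The 54 follows from the plan's own recruitment and dropout figures. The correlations are assumptions. The 1% level is taken from section 4.3, since section 4.11 states none.

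**What to change.** In section 4.11, replace the conditional sentence with:

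> One value per child is analysed whatever the inter-eye correlation: the mean of the right- and left-eye change in SER (and in AL).

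This fixes the unit in advance, agrees with the per-child sample size, lets the listed tests run on independent observations, and uses readings that the schedule already provides for both eyes. It needs no extra visit, measurement or child. The one small downside is that results are less directly comparable with reports based on right eyes.

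If the sponsor values that comparability more, the alternative is to state right eye only, without the condition. That also removes the data-dependent choice, but gives no gain in precision.

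### Welch's correction depends on an unnamed test of SDs, and the plan does not say whether it covers the 24-month t tests of SER and AL; use Welch throughout

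*Combined protocol and SAP*

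**What the plan says.** The opening paragraph of section 4.11 states: "Baseline data between two groups between males and female will be analyzed by unpaired t-tests". The next sentence is the rule at issue: "Welch correction is applied if the difference of SD between the groups is statistically significant". No test of SDs is named and no level is given.

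The outcomes are analysed further down, in point 1 of the same section. The main comparison is this: "Repeated measures ANOVAs were used to compare the changes from the baseline visit in SER, and AL over time and between the two study groups". If the group effect and the time-by-group interaction are both significant, unpaired t "tests were used to test for differences in SER, AL, between the two groups after the 24-month follow up period", with Bonferroni correction for post hoc comparisons. Welch is not mentioned there. Point 3 applies the same methods to choroidal thickness.

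Two other sections bear on arm sizes. Section 4.3 plans 90 children per group and allows for about 40% dropout. Section 4.5 states: "A simple randomization will be adopted in this study".

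**The concern.** Two things are unsettled. First, a preliminary significance test on the same data chooses between the pooled and the Welch t test. At this sample size such a test often misses a real difference in spread, and the pooled test is then kept where it does not fit. Second, a reader cannot tell which t tests the sentence governs. By position it belongs to the baseline comparisons. On that reading the 24-month t tests have no provision for unequal variances.

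The pooled t test goes wrong when arm sizes and SDs differ together. It rejects too often if the smaller arm has the larger SD, and too seldom in the reverse case. Both conditions are possible here. Simple randomisation and dropout can leave unequal arms, and a lens that slows progression may also narrow its spread. At stake is the size of the 24-month t test and the accuracy of its standard error.

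**Working it through.** **Inputs from the documents (section 4.3).** Difference 0.50 D, one common SD of 0.6 D, two-sided alpha 0.01, power 90%, 43 completers per group, about 40% dropout, 90 per group recruited. Section 4.11 gives no significance level, so 0.01 is carried over from section 4.3.

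**Assumptions, not in the documents.** SD 0.6 D in the single vision (SV) arm and 0.45 D in the MS arm, a ratio of 1.33. Completers split 48/60, 40/60 or 60/48 (SV/MS). SD pre-test: a two-sided F test at 0.05.

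**1. The plan's own figure.** n = 2(z₀.₉₉₅ + z₀.₉₀)²σ²/δ² = 2(2.576 + 1.282)² × 0.36/0.25 = 42.9, so 43. This reproduces the plan. The noncentral t version gives 45. Dividing by 0.6 for dropout gives 72 and 75, the plan's range.

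**2. How unequal can the arms become?** With 180 children under simple randomisation, the 95% limits for one arm are 90 ± 1.96√45 = 90 ± 13, or 77:103. With 108 completers (60% of 180) they are 54 ± 1.96√27 = 54 ± 10, or 44:64.

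**3. Standard error under pooling.** The pooled variance is s² = [(n₁−1)0.36 + (n₂−1)0.2025]/(n₁+n₂−2), and the pooled SE is √[s²(1/n₁ + 1/n₂)]. The true SE is √(0.36/n₁ + 0.2025/n₂).

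| SV/MS | s² | Pooled SE (D) | True SE (D) | Ratio |
|---|---|---|---|---|
| 54/54 | 0.2813 | 0.1021 | 0.1021 | 1.000 |
| 48/60 | 0.2723 | 0.1011 | 0.1043 | 0.969 |
| 40/60 | 0.2652 | 0.1051 | 0.1112 | 0.945 |
| 60/48 | 0.2902 | 0.1043 | 0.1011 | 1.032 |

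The pooled SE is about 3% too small at 48/60, about 6% too small at 40/60, and about 3% too large at 60/48.

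**4. Error rate of the stand-alone t test at nominal 0.01** (normal data, 1,000,000 simulated trials per row):

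| SV/MS | Pooled | Two-stage | Always Welch |
|---|---|---|---|
| 48/60 | 0.0128 | 0.0110 | 0.0102 |
| 40/60 | 0.0150 | 0.0119 | 0.0102 |
| 60/48 | 0.0080 | 0.0095 | 0.0101 |

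At nominal 0.05 and 40/60 the three are 0.064, 0.055 and 0.050. At 54/54 the pre-test finds the SD difference in 54.5% of trials, or 25.9% if the MS SD is 0.5 D.

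**5. Range of the two-stage rule** (nominal 0.01, SD ratios up to 1.5 in either direction). Equal arms (90:90, 54:54, 43:43): about 0.010. 77:103: 0.0093 to 0.0109. 44:64: 0.0088 to 0.0116. 54:90: 0.0087 to 0.0119. 43:90: 0.0082 to 0.0130. If the SD test is run at 0.01, 54:90 widens to 0.0078 to 0.0131.

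**6. Power cost of always using Welch when SDs are equal** (0.50 D, alpha 0.01). 43/43: 88.76% pooled against 88.74%. 48/60: a loss of 0.05 points. 40/60: 0.19 points. 43/90: 96.89% against 96.64%, a loss of 0.25 points. At 43/90 with a 0.30 D difference and alpha 0.05: 76.33% against 75.97%, a loss of 0.36 points.

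**The case against.** A reader might infer that the primary comparison fails to hold its error rate. The documents do not support that, for three reasons.

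- The rule directly follows the baseline t tests, which decide no efficacy claim.
- The main comparison of SER and AL is a repeated measures ANOVA, to which the Welch sentence does not apply and which the fix leaves untouched.
- The 24-month t test runs only after a significant group effect and a significant interaction, and with Bonferroni correction. Further conditions can only lower its rejection rate. A simulation of the gated sequence, with an assumed serial covariance and no Bonferroni correction, gave at nominal 0.01 rates of 0.0062 pooled and 0.0060 two-stage at 48/60, and 0.0083 and 0.0074 at 40/60. All are below nominal.

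The error also needs unequal arms and unequal SDs together. The documents give one SD and a 90:90 plan, and with equal arms the error is nil. Nor is Welch entirely free: the power loss exceeds 0.1 point once the arms are clearly unequal.

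All of this stands, and it limits the point to the t test itself. It does not settle which t tests the sentence covers, and it gives no reason to keep a pre-test whose method and level are unstated. The narrow reading, under which the rule stops at baseline, is the less favourable one for the 24-month tests if they are then pooled.

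**Conclusion.** The point holds in a limited form and is minor. The plan makes Welch conditional on an unspecified test of SDs and does not say whether the 24-month t tests of change in SER and AL fall under that rule. On one reading those tests have a true level of about 0.011 to 0.012 at nominal 0.01. On the other, if pooled, it is about 0.013 to 0.015, or 0.008 if the arm with the larger SD is the bigger one. These figures rest on assumed SDs of 0.6 and 0.45 D, assumed splits of 48/60, 40/60 and 60/48, normal data, and an assumed F pre-test at 0.05. They apply to the t test taken alone. Inflation of the overall primary decision is not claimed, and no sample size figure changes.

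**What to change.** Replace the Welch sentence in section 4.11 with:

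*All unpaired t tests, including the 24-month comparisons of change in SER and AL, use Welch's unequal-variance form, and no preliminary test of SDs is done.*

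This settles the scope, removes the data-driven choice, and holds the t test at its nominal level in every scenario examined. The cost is one sentence and, if the SDs are in truth equal, the small loss of power in step 6 of the working: under 0.1 point at near-equal arms, about 0.2 points at 40/60, and up to about 0.4 points at the extreme of 43/90.
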